4.2 Schedule of Visits and Assessments

The schedule of event table:

Visit Number Day Time Window (days)	Screening	Treatment Period							Follow-Up		
	1 -7 to -2	2 1	3 8 ±1	4 15 ±1	5 22 ±1	6 29 ±1	7 36 ±1	8/EOT ⁷ 43 ±1	9/FU 50 ±1	10/FU 57 ±1	Phone/FU 71 ±1
Informed Consent ¹	X										
Informed Consent for Pharmacogenomics ²	X										
[REDACTED]	X										
Demographics	X										
Medical history	X										
Inclusion/exclusion criteria ³	X	X									
Physical examination	X	X		X		X		X ⁷		X	
Vital signs (seated)	X	X	X	X	X	X	X	X ⁷	X	X	
Laboratory tests	X	X	X	X	X	X	X	X ⁷	X	X	
Pregnancy test (as applicable) ⁹	X	X						X			
12-lead ECG	X		X			X		X ⁷			
SD-OCT	X	X	X	X	X	X	X	X ⁷	X	X	
FP/FA	X							X ⁷			
Visual acuity	X	X	X	X	X	X	X	X ⁷	X	X	
Slit-Lamp	X	X	X	X	X	X	X	X ⁷	X	X	
IOP	X	X	X	X	X	X	X	X ⁷	X	X	
Administration of study agent ⁴		X	X	X	X	X	X	X ⁷			
Dispense study agent		X	X	X	X	X	X				
Study agent accountability		X	X	X	X	X	X	X ⁷			
Pharmacokinetic (PK) blood sample (for plasma extraction)		X ⁵	X ⁶	X ⁶	X ⁶	X ⁶	X ⁶	X ^{5,7}	X		
Biomarker plasma aliquots		X ⁵				X ⁵		X ^{5,7}	X ⁵		
[REDACTED]		X ²									
Adverse events ⁸	X	X	X	X	X	X	X	X ⁷	X	X	X
Concomitant/current medications ⁸	X	X	X	X	X	X	X	X ⁷	X	X	X
Trial completion											X

1. All subjects must sign an informed consent consistent with ICH-GCP guidelines prior to any trial related procedures, which includes medication washouts and restrictions.
2. [REDACTED]
3. A preliminary check of inclusion/exclusion criteria will be performed at screening (Visit 1) after obtaining informed consents.
4. Study agent will be self-administered in the clinic under supervision of study personnel during every visit of the treatment period (Visits 2-8) following all safety and ophthalmic assessments. Training on study agent administration will be conducted prior to the initial study agent administration at Visit 2.
5. A pre-dose PK blood sample will be taken to be centrifuged for collection of plasma samples. Biomarker plasma aliquots will be obtained from the PK samples. At Visit 2 only, four post-dose PK blood samples will be taken.
6. A pre-dose PK blood sample will be taken to be centrifuged for collection of plasma samples.
7. End of Treatment (EOT) visit (Visit 8): all study related procedures will be conducted at the conclusion of 6 weeks of treatment on Day 43 ±1. Withdrawal of consent is allowed at any time. For subjects who withdraw consent from the study, no study procedures will be done thereafter. For those that withdraw from the study agent, follow-up visits are to occur as per the protocol. Excluding cases of medical emergency, but prior to the discontinuation of a subject from the clinical study for disease worsening, the study investigator should discuss each case of discontinuation with the sponsor.
8. Adverse events and concomitant medications will be assessed at every study visit as well as recorded at any unscheduled subject contact (e.g., unscheduled phone calls, etc.). Following completion of study agent treatment (Visits 2-8), all current medications will be assessed in the follow-up period.
9. Pregnancy test required in **Poland only** per Inclusion Criteria.

5. Study Treatments

This is a single arm, open-label study. All subjects will receive the investigational treatment ALK4290 at a daily dosage of 800 mg administered orally twice a day as 400 mg tablets for 6 weeks.

6. Sample Size and Power Considerations

A total of 30 subjects will be enrolled in the study with the intent of obtaining approximately 25 evaluable subjects who would complete at least 3 weeks of treatment and evaluations through Visit 5 (Day 22). Subjects who discontinue prior to Day 22 may be replaced. Subjects who withdraw or are withdrawn during screening (prior to completing V2) will be replaced. The study is not powered for detecting statistically significant differences in therapeutic parameters in subjects with wAMD receiving ALK4290.

7. Data Preparation

Data management procedures, including database design and selection of the data dictionary will be performed by the Data Manager and reviewed and approved by the Sponsor. Auto-coding of all AEs, medical histories and concomitant medications will be performed by the IBM Clinical Development EDC system with additional manual coding performed by the Sponsor designated medical coder. Medical coding will be reviewed by the GCT Medical Monitor and confirmed and approved by the Sponsor. All reported study data will be recorded on the electronic Case Report Forms (eCRF) using IBM Clinical Development and transferred to SDC by ProTrials. Clinical personnel at the study site and the CRO are responsible for ensuring that the protocol is followed and that the eCRFs are properly completed.

Additional safety lab data external to the eCRF data will be provided by Synevo to ProTrials to be reconciled with the EDC data and transferred separately to SDC for analysis. External PK data will be transferred from KCAS and will be analyzed by SDC as outlined in the PK plan (separate from the SAP).

[REDACTED]

[REDACTED]

All Subject IDs will be assigned automatically within the EDC. The Subject ID consists of 9 numbers: the first set of 3 numbers are specific for the protocol number (i.e., 202); the second set of 3 numbers are specific for the site number (i.e., 001 through 012), and the third set of 3 numbers are the subject specific screening number (e.g., 001, 002, etc.).

After data are entered into EDC, data are reviewed and verified by the clinical monitoring/operations CRO and ProTrials Data Management. Additionally, SAE reconciliation of the Clinical Database is performed against the Alkapest Global Safety Database and any issues are resolved. When the database has been confirmed to be complete, consistent and accurate, the database will be locked according to ProTrials Standard Operating Procedures and study specific Data Management Plan. Any

Unless specified otherwise, all ocular assessments and efficacy outcome measures are with respect to the study eye, here hence. Data collected for the fellow eye (non-study eye) will be included in subject listings and may be analyzed.

Study day will be calculated as (Date of Visit) – (Date of Initiation of Investigational Medicinal Product [IMP]) + 1 for visits after initiation of IMP and as (Date of Visit) – (Date of Treatment Initiation) for visits prior to initiation of IMP.

9.1 Missing or Inconclusive Data Handling

In general there will be no imputation of missing data other than for partial or missing dates. Partial start and end dates for medical history, concomitant medications, and AEs will be imputed as outlined in [Appendix 1](#). Completely missing dates will only be imputed for AEs.

The original dates will be displayed in data listings along with the relative study day for complete dates. imputed dates will be used in derivations only (e.g., to determine treatment-emergence status, etc.).

9.2 Definition of Baseline

Baseline measures are defined as the last measure prior to the initiation of study treatment, usually at Visit 2 (Day 1). For assessments that are not performed at Visit 2 (i.e. FP and FA), the screening Visit 1 measures will be considered as baseline.

9.3 Visit Windows and Visit Mapping

The following table lists the scheduled visits and planned study day along with the corresponding visit window that will be used to map visits occurring outside of the scheduled times.

Scheduled Visit	Planned Study Day	Visit Window
Visit 1 / Screening	Day -7*	<= Day -1
Visit 2	Day 1	Day 1
Visit 3	Day 8	Day 2 to Day 11
Visit 4	Day 15	Day 12 to Day 18
Visit 5	Day 22	Day 19 to Day 25
Visit 6	Day 29	Day 26 to Day 32
Visit 7	Day 36	Day 33 to Day 39
Visit 8 / End of Treatment (EOT)	Day 43	Day 40 to Day 46
Visit 9 / Follow-Up (FU)	Day 50	Day 47 to Day 53
Visit 10 / FU	Day 57	Day 54 to Day 60
Phone / FU	Day 71	>=Day 61

* Visit 1/Screening of Fundus Photography/FA can be performed up to Day -14, per the protocol.

Summary tables will be presented by scheduled visit using the following algorithm. If there are multiple non-missing assessments within a visit window, then the visit closest to the scheduled visit will be used. If multiple visits are equidistant from the scheduled visit, then the scheduled visit and unscheduled visit

will be selected in that order. If multiple visits of the same type are equidistant from the scheduled window, then the earliest visit of that type will be selected.

Subject listings will include all visits.

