**8 INVESTIGATIONAL PLAN**

**8.1 VISIT SCHEDULE**

All study agent administrations at the study site will be done under the direct supervision of the study personnel for documentation of precise administration times. In case a visit is delayed beyond the window detailed in [Section 15.1, Schedule of Events Table](#), the delayed visit should be scheduled as soon as possible and documented with the actual date and the reason for the delayed visit. The next visit should still take place at the time it was originally scheduled in this treatment course. Any delays in visit dates, outside of the defined criteria in the Schedule of Events Table, will be reported as a protocol deviation.

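### SAP 9.3 assigns visits by study day alone, so an end-of-treatment visit held on Day 47 or later leaves the Visit 8 primary BCVA analysis and is filed as follow-up Visit 9

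*SAP*

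**What the plan says.** SAP 9.3 tabulates, for each scheduled visit, a planned day and a "visit window that will be used to map visits occurring outside of the scheduled times". Visit 8/EOT (planned Day 43) has "Day 40 to Day 46" and Visit 9 (planned Day 50) has "Day 47 to Day 53". Within a window the rule is: "If there are multiple non-missing assessments within a visit window, then the visit closest to the scheduled visit will be used". On a tie, a scheduled visit is preferred to an unscheduled one. After that, "If multiple visits of the same type are equidistant from the scheduled window, then the earliest visit of that type will be selected". The section ends: "Subject listings will include all visits".

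Protocol 8.1 has a delayed visit rebooked promptly and reported as a deviation, and adds: "The next visit should still take place at the time it was originally scheduled in this treatment course". The schedule (Protocol 15.1, repeated in SAP 4.2) puts EOT at Day 43 ±1 and Visit 9 at Day 50 ±1. FP/FA is done only at screening and at Visit 8.

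SAP 14 defines the primary endpoint as the BCVA change from Visit 2 to Visit 8 / Day 43 in the Evaluable set, tested with a one-sample t-test at two-sided alpha 0.20. SAP 9.1 states: "In general there will be no imputation of missing data other than for partial or missing dates".

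**The concern.** Taken together, these rules can remove a primary-endpoint value that was actually measured. If EOT slips to Day 47 or later, its study day lies in the Visit 9 window. The real Visit 9 has not moved, so it normally falls in the same window, and usually closer to Day 50. The Visit 8 cell is then empty and stays empty.

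Protocol 10.3 makes a subject evaluable after at least 3 weeks of treatment. Such a subject therefore still counts as evaluable but gives no value to the primary t-test. The loss comes from a label and not from any judgement about data quality.

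The SD-OCT measures follow the same path. SAP 17.1 analyses the quantitative ones in the same manner as the primary endpoint. It also aims to describe duration of action. That aim is blurred whenever an EOT value takes the Visit 9 slot and is read as a follow-up result. For FP/FA, the single post-baseline record would no longer sit under EOT.

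**Working it through.** **1. The windows reproduce.** Midpoints between planned days are (36 + 43)/2 = 39.5, (43 + 50)/2 = 46.5 and (50 + 57)/2 = 53.5. They give Day 40–46 for Visit 8 and Day 47–53 for Visit 9, exactly as tabulated.

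**2. How late EOT must be.** The protocol window for EOT ends on Day 44. Day 45 or 46 is a deviation but still maps to Visit 8. The problem begins on Day 47, which is 47 − 44 = 3 days past the limit.

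**3. BCVA in the Visit 9 window.** The distance to the planned day is |day − 50|. Both visits are treated as scheduled, so a tie goes to the earlier one. With the real Visit 9 inside its protocol window and after EOT, the value selected for the Visit 9 row is:

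| EOT day (distance) | Visit 9 on Day 49 (1) | Day 50 (0) | Day 51 (1) |
|---|---|---|---|
| 47 (3) | real Visit 9 | real Visit 9 | real Visit 9 |
| 48 (2) | real Visit 9 | real Visit 9 | real Visit 9 |
| 49 (1) | – | real Visit 9 | tie: EOT kept |

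The real Visit 9 wins in 7 of 8 combinations. In the eighth, the EOT value is shown as Visit 9 and the real Visit 9 is left out. The EOT value also takes the Visit 9 row in these cases:
- there is no Visit 9;
- EOT is on Day 50 or later (up to Day 52) and Visit 9 follows within the window;
- Visit 9 is late (EOT 47 with Visit 9 on 53; EOT 48 with 52 or 53; EOT 49 with 52 or 53).

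**4. BCVA in the Visit 8 window.** In every case with EOT on Day 47–52, the Visit 8 row holds no EOT value. It is empty unless some other visit, such as a late Visit 7 or an unscheduled one, falls in Day 40–46. For EOT on Day 44–46 the value stays in Visit 8 in every case.

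**5. FP/FA.** Selection is made among non-missing assessments, and Visit 9 has no FP/FA (Protocol 8.2.4.1). A late angiogram is displaced in 0 cases. It is relabelled Visit 9 and is absent from the EOT row. The FA tables in SAP 24 are by scheduled visit, and the SAP does not say whether they would print a Visit 9 row.

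**6. Size.** The documents give no SD, effect size or frequency of late visits. I take 25 evaluable subjects (SAP 6) as the starting number and hold SD constant. The mean change needed for p = 0.20 equals the 80% CI half-width, t(0.90, n − 1) × SD/√n.

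| Visit 8 values | Half-width (SD units) | Ratio to n = 25 | SE ratio √(25/n) |
|---|---|---|---|
| 25 | 0.2636 | 1.000 | 1.000 |
| 24 | 0.2693 | 1.022 | 1.021 |
| 23 | 0.2755 | 1.045 | 1.043 |
| 22 | 0.2821 | 1.070 | 1.066 |

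Each lost value is 1/25 = 4% of the target number.

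**The case against.** Contiguous midpoint windows are a legitimate prespecified choice, and Day 47 is indeed nearer to Day 50 than to Day 43. One can also argue that the mapping is meant for unscheduled assessments. SAP 16.5 uses it that way for ECGs, and nothing in 9.3 expressly says that a scheduled visit loses its label. On that reading nothing is lost. But 9.3 does not limit itself to unscheduled visits, and its tie rule ranks scheduled against unscheduled ones, so both types compete. What stands is that the text is open to two readings; the literal one removes the value.

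Two stronger readings are tempting, and the documents support neither.
- A reader might infer that the only post-baseline angiogram is discarded. It is not, because it has no competitor at Visit 9.
- A reader might infer that an on-drug value is being thrown away. Visit 8 includes a supervised dose after the assessments, but treatment is planned to end at Day 43 ±1 and the bottle contents are not visible in the public text. Whether study agent lasts beyond Day 46 cannot be checked. If it had run out, leaving the value out of a 6-week on-treatment row would be defensible.

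The reach is also limited. Delays of this length are reportable deviations. The values remain in the listings, the repeated-measures model still uses the subject's other visits, and the study is stated not to be powered.

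Finally, a remedy that simply honoured the EOT label on any study day would do harm. Subjects who stop study agent also have EOT procedures (Protocol 8.2.3). If these were done at the time of stopping, an assessment well before Day 40 could enter the Day 43 analysis, in effect carrying an early value forward. Any fix therefore needs a lower bound.

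**Conclusion.** The concern holds in a limited form. Read literally, SAP 9.3 takes the BCVA of an EOT visit held on Day 47 or later out of the Visit 8 t-test in every case, unless another visit fills Day 40–46. An on-time Visit 9 then usually replaces it in the Visit 9 row (7 of 8 combinations for EOT on Day 47–49). Otherwise an end-of-treatment value stands as follow-up. FP/FA is relabelled, not displaced, and goes missing from the EOT row. The word lost applies to the by-visit summaries and the t-test only.

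The cost is about 2% on the mean change needed for p = 0.20 if one of 25 values is lost, and about 7% if three are. These counts are illustrations, since no frequency is given; they also assume an unchanged SD. The effect is probably small. It is still worth correcting, because it touches the primary time point, the correction is almost free, and leaving it open invites a choice after the data are seen in an open-label trial.

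**What to change.** Add to SAP 9.3:

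- A nominal Visit 8/EOT assessment done after Day 46 keeps its Visit 8 label for the Day 43 BCVA, SD-OCT and FP/FA analyses if study agent was still being taken up to that visit, meaning a last dose on that day or the day before according to the dosing records. It then does not compete in the Visit 9 window. Judge this on the last dose before the assessments; the supervised Visit 8 dose comes after them and should not satisfy the condition by itself.
- The exception does not apply to EOT or early-termination assessments before Day 40, which stay mapped by study day.
- A sensitivity analysis of the primary endpoint is limited to assessments on Day 40–46.

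The one-day limit is an analysis choice and does not come from the documents; the sponsor should confirm it before the data are reviewed.

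The cost is a few sentences and one repeat of the primary table, with no new data, since SAP 13 already uses the date of last dose. The downside is that a few EOT values would reflect slightly more than 6 weeks of treatment, which the sensitivity analysis would show.

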9.4 Data Analysis Conventions

Quantitative variables will be summarized using descriptive statistics including the number of observations (n), mean, standard deviation (SD), median, minimum, and maximum values. Means, medians, and confidence intervals (CI) will be reported to two decimal places and SDs to three. Summaries for discrete variables will include frequency counts and percentages. All percentages will be rounded to one decimal place (i.e., XX.X%). Change from baseline will be calculated as the value at follow-up visit minus baseline.

The primary efficacy analysis will be evaluated at a two-sided significance level of 0.20. All p-values will be rounded to four decimal places; p-values less than 0.0001 will be presented as “<0.0001”; p-values greater than 0.9999 will be presented as “>0.9999”.

9.5 Adjustments for Multiplicity

There will be no adjustments for multiplicity for this early phase, exploratory study.

10. Disposition of Subjects

Subject disposition will be presented in terms of the numbers and percentages of subjects who were enrolled, treated, completed the study, and discontinued from the study.

The number and percentage of subjects discontinued from the study and the reasons for study discontinuation will be summarized for all enrolled subjects. The reasons for study discontinuation that will be summarized include: AEs, treatment with prohibited concomitant medications, subject non-compliance, withdrawal of consent, pregnancy, termination of study, and other. A subject listing will be provided that includes the date (and study day) of and reason for premature study discontinuation.

The number and percentage of subjects with protocol deviations will be summarized for the ITT set. A subject listing will be provided that includes the date of the deviation and the deviation description.

Subject listings will be provided to list out informed consent dates, inclusion and exclusion criteria violations, and exclusions from the PP set.

11. Demographic and Baseline

11.1 Demographic and Vital Signs

Demographic variables collected in this study include age in years (at time of screening), sex, race, ethnicity, body mass index (BMI), weight, height, iris color, and study eye (OD or OS). Subjects who record more than one race will be grouped into a single category denoted as 'Multiple Race'.

Age (years) will be summarized using continuous descriptive statistics. Age will also be categorized as follows: <65 years and ≥65 years.

The number and percentage of subjects will be presented for age category, sex, race, ethnicity, iris color and study eye (OD or OS). Percentages will be based on the total number of subjects in the ITT set. A subject listing that includes all demographic variables will be provided.

11.2 Baseline Characteristics

Baseline BCVA letter score as measured by the ETDRS testing method; CST, presence and height of IRF, SRF, and PED as measured by SD-OCT; and presence and size of CNV and leakage from CNV as measured by FP/FA will be included in the relevant summaries (including the demography summary) and listings.

Prior anti-VEGF IVT treatments will be collected at Screening (Visit 1) for which a subject listing will be provided.

12. Medical History and Concomitant Medications

12.1 Medical History

Medical history will be summarized using discrete summary statistics and presented at the subject level by system organ class (SOC) and preferred term (PT). If a subject reports the same PT multiple times within the same SOC, that PT will only be counted once within that SOC. As with the PT, if a subject reports multiple conditions within the same SOC, the SOC will only be counted once. Separate tables will be created for ocular and non-ocular medical history. Medical history will be coded using MedDRA, Version 21.0. The summaries will be based on the ITT set.

Listings of relevant medical history, including prior medical history within three months prior to Visit 1 (Screening) will be captured in the appropriate eCRF. A subject listing of reported medical history with start and stop dates (or ongoing) will be provided.

12.2 Prior and Concomitant Medications/Treatments

At the screening Visit 1 (Day -7 to Day -2), subjects will be asked what medications they are taking, as well as those the subject may have taken prior to screening. At each subsequent study visit, subjects will be asked what concomitant medications they are currently taking or if there have been any changes to their medication since the previous visit.

All prior and concomitant ocular and non-ocular medications will be listed using the ITT set including generic name, route of administration, start date, stop date, dosage, and indication. Prior and concomitant medications will be categorized by WHO Drug Dictionary (B3 Global March 2018 or higher) classification for therapeutic class and drug name.

Counts and percentages of ocular and non-ocular concomitant medications will be summarized separately, and summaries will be displayed for the ITT set. Subjects with multiple medications in the same WHO drug dictionary class or preferred name will be counted only once for that respective WHO drug dictionary class or preferred name.

13. Dosing Compliance and Treatment Exposure

13.1 Dosing Compliance

A dose is considered a single 400 mg tablet. Subjects are instructed per protocol to administer a dose twice daily (i.e., once in the morning and once in the evening). Dosing compliance (% compliance) will be assessed by calculating the number of actual doses received and comparing that to the number of expected doses as follows:

$$\text{Compliance (\%)} = \frac{\text{Number of Actual Doses Received}}{\text{Number of Expected Doses}} \times 100$$

The number of actual doses received will be calculated from the number of dispensed and returned tablets as recorded in the eCRF. The number of expected doses that will be used for calculating compliance will be calculated as $\{2x [\text{date of last dose} - \text{date of first dose}] + 1\}$ for all subjects, regardless of study completion status. Overall compliance will also be categorized as compliant ($\geq 75\%$) and non-compliant ($< 75\%$).

Treatment compliance (%) will be summarized for the Safety set using continuous descriptive statistics. The compliance categories defined above will be summarized with counts and percentages.

A subject listing of compliance will also be produced.

